- **CLINICIAN WITHDRAWAL:** Clinician took participant off protocol treatment (PMRT). Please note that after taking a subject off protocol treatment, study questionnaires and follow-up CONTINUE through the 10-year follow up period. Site study staff should complete all Medical Record Abstraction CRFs and Follow-up CRFs.
- **DEATH:** If a study participant dies, the site staff should complete all Medical Record Abstraction CRFs through death. After all data has been collected through death, sites may take participant off study by submitting the Off-Study CRF via InForm.
- **FOUND TO BE INELIGIBLE:** Participant was enrolled on the trial but was later found to be ineligible. Select one:
 - a. Yes, protocol treatment (PMRT) will continue [treating physician and study chairs agree there are no safety concerns if the patient continues protocol treatment].
 - b. No, protocol treatment will not continue [in this case, study questionnaires and follow up should continue through the 10 year follow up period. Site study staff should complete all Medical Record Abstraction CRFs no matter how long the subject actually received protocol treatment].
- **SWITCHED ARMS:** If inhomogeneity constraints are not attainable in the hypofractionated setting, the patient will be treated with standard fractionation as per protocol. Switching arms in this case is permitted, and these participants who switch arms will still be asked to complete all patient questionnaires and will be followed for 10 years
- **OTHER:** Please specify.
 - **Note:** If a participant experiences a distant recurrence, they should be withdrawn from the study by selecting this option in InForm. Once participants are withdrawn from the study due to distant recurrence, all follow-up should be discontinued.

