10. STATISTICAL CONSIDERATIONS

10a. Accrual: Based on previous years' treatment records, we anticipate that there will be about 40-50 eligible patients per month across the multiple participating academic and community centers. The accrual rate of this study is expected to be about 22 patients per month. We expect conservatively (based on survey data) that 75% of the eligible patients (after confirmation of the need for radiation therapy) are willing to be randomized to either the long-course or short-course treatment. The accrual will be open until 400 patients are enrolled. Randomization will be stratified by treatment center and age of the patient (<45 vs. ≥45). We expect the proportion of patients in the younger cohort of the study sample to be 40%. The anticipated length of the accrual period is 21-27 months.

10b. Statistical analysis plan for patient-reported quality of life outcomes and power considerations

Quality of life (QoL) measurement and the primary endpoint: We will use an array of instruments to rigorously assess quality of life among study participants, such as the FACT-B scores, satisfaction with breast surgery outcomes (BREAST-Q), Lymph-ICF, and financial burden. We will record and report all reasons for dropout and which outcomes were not reported, and include this data in our final reports. FACT-B (version 4) specifically measures quality of life in breast cancer patients and includes modules for assessing physical well-being, emotional well-being, social well-being, functional well-being and a 2-item question characterizing a breast cancer patient's relationship with her physician. QoL will be assessed at baseline, 6 months, 12

months and 18 months. This data will allow peer reviewers and readers of our publications to assess the validity of our study.

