To determine the primary endpoint among those measurement scales, we surveyed patients who had undergone radiation therapy after mastectomy and immediate reconstruction and found that the majority of chose **the Physical Well-Being (PWB) subscale of the FACT-B (version 4) to be the most important element of their quality of life, regardless of age** (data not shown, manuscript in preparation). Based on this result, we selected the FACT-B PWB score as the primary endpoint of this study. To adjust for QoL at baseline, we will compare change in PWB score (relative to each patient's pre-radiation score) between the short and long-course treatment groups, instead of comparing PWB scores between the two groups.

Statistical analysis of the primary endpoint and power: As per the intention-to treat principle, the primary analysis population will be all women who are randomly assigned to receive either short-course or long-course (conventional) radiation therapy. The secondary analysis population will be the per-protocol cohort. We hypothesize that the short-course radiation therapy will lead to improved PWB scores compared to the conventional long-course treatment. To confirm this hypothesis, we will use Analysis of Covariance (ANCOVA) models. **Change in the FACT-B PWB subscale (7 items) score at 6 months relative to baseline** will be the response variable, and the intervention group indicator (long-course versus short-course radiation therapy) and age group (below 45 vs. 45 or above) will be included in the ANCOVA model as independent variables. Using change in the PWB score relative to baseline will give us a more normal distribution of outcomes, versus using the score itself. **The age threshold of 45 years was selected by our patient advocates.**

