Under the same setting as shown described above, “**Table: N=400 randomized patients, $\alpha=0.05$** ” reveals the power to detect an age interaction will be 59%-89%. These are conservative estimates for the 6-month change in PWB, given that patients in our survey were interviewed between 6 and 24 months (data not shown, manuscript in preparation), and there may be some recovery in physical symptoms with time.

Table: N=400 randomized patients, $\alpha=0.05$.				
PWB score Δ		SD of Δ	Power	
Younger patients	Older patients		Main analysis	Interaction
4.0	2.0	3.5	>0.99	0.80
4.0	2.0	4.0	>0.99	0.69
4.0	2.0	4.5	>0.99	0.59

Strategy for handling missing data: Given the patient incentives, short time required to complete surveys, and enthusiasm voiced by the patients we surveyed, we expect that the dropout fraction from the study at 6 months will be at most 5% and that the dropout mechanism would be mostly random. In a primary analysis, we will exclude those who dropout from the study or who do not have data at 6 months. However, because a random missing mechanism assumption is not verifiable empirically, we will use several methods to handle missing observations to confirm the stability of the findings from the primary analysis. Specifically, we will perform the following: (1) last observation carried forward (LOCF), (2) mean value imputation, (3) worst-case and (4) best-case imputation. We will also conduct (5) multiple imputation⁵¹. For multiple imputation, we will create 10 complete datasets, imputing the missing values using chained equations. We will perform the analysis with the 10 complete datasets and integrate the results with Rubin’s method of imputation.⁵¹ For another approach, we will analyze this data according to (6) the methods described in Schluchter and in Schluchter, Greene and Beck.^{52,53} These methods take into account the possibility of informative “missingness” by jointly modeling the longitudinal responses (here, QoL scores) and the time to dropout.

Other QoL analysis: In secondary analyses, we will use generalized estimating equation (i.e., marginal modeling) and random-effects models to analyze longitudinal data⁵⁴ (i.e., baseline, 6 months, 12 months and 18 months) for the FACT-B total score (37 items) and each subscale as well as the primary endpoint (FACT-B PWB subscale).

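### The primary analysis is called intention-to-treat on all randomised women but is run on complete cases with only arm and age group in the model; the two statements must be reconciled, and two of the six missing-data checks add little

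*Combined protocol and SAP*

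**What the plan says.** Under intention to treat, Section 10b states that "the primary analysis population will be all women who are randomly assigned to receive either short-course or long-course (conventional) radiation therapy". The response is "Change in the FACT-B PWB subscale (7 items) score at 6 months relative to baseline", and besides the treatment indicator only "age group (below 45 vs. 45 or above) will be included in the ANCOVA model as independent variables". Baseline physical well-being (PWB) is subtracted to form the change score but is not a covariate.

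The missing-data paragraph of the same section then says: "In a primary analysis, we will exclude those who dropout from the study or who do not have data at 6 months". It expects at most 5% dropout at 6 months, mostly random, and concedes that randomness cannot be verified from the data. Six sensitivity analyses follow. They begin with "1) last observation carried forward (LOCF), (2) mean value imputation" and continue with worst-case imputation, best-case imputation, multiple imputation by chained equations (10 datasets), and a joint model of quality of life and time to dropout. Random-effects models of all four visits are planned as secondary analyses.

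Section 8 adds one route to missing data that depends on health: "Once participants are withdrawn from the study due to distant recurrence, all follow-up should be discontinued".

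**The concern.** A population of all randomised women and a rule that removes those without a 6-month score cannot both describe the primary analysis. As written, no primary estimate covers everyone randomised.

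The removal happens after randomisation and need not be random. Distant recurrence ends follow-up. Radiation may start up to 4 months after randomisation (Section 5.2), and the 6-month visit is counted from its start (Section 9.1), so a woman who never starts has no defined 6-month date. The primary model can absorb missingness that depends on arm or age group, but not missingness that depends on baseline PWB or on later health.

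At stake is whether the headline contrast estimates the effect in all randomised women, and whether the listed checks would show it if it did not.

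**Working it through.** **The plan's own figure.** Inputs from Section 10b: 200 per arm, difference 2.8, SD of change 4.0, two-sided 0.05. SE = 4.0 × √(2/200) = 0.40, and 2.8/0.40 = 7.0, so power exceeds 0.99. This reproduces the power table but not the 93% in the text, which is a separate discrepancy. With 5% lost (190 per arm), SE = 4.0 × √(2/190) = 0.41 and power still exceeds 0.99. Lost power is not the problem; bias is.

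**Bias of the complete-case contrast (short minus long).** Let f be the fraction missing in an arm and g the number of points by which the missing women's change is worse than the observed women's. The observed mean exceeds the all-randomised mean by f × g, so

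bias = f_short × g_short − f_long × g_long.

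The documents give only the 5% overall ceiling. The split between arms and the values of g are assumptions. With the same g in both arms:

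| Missing short / long | Overall | g = 2 | g = 4 | g = 8 |
|---|---|---|---|---|
| 5% / 5% | 5% | 0 | 0 | 0 |
| 2% / 8% | 5% | −0.12 | −0.24 | −0.48 |
| 0% / 10% | 5% | −0.20 | −0.40 | −0.80 |
| 5% / 15% | 10% | −0.20 | −0.40 | −0.80 |

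Reversing a split reverses the sign. If instead both arms lose 5% but the gaps differ by 2 to 6 points, the bias is 0.05 × 2 = 0.10 to 0.05 × 6 = 0.30.

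As a rough guide to g from baseline alone: with the plan's correlation of 0.65 to 0.70 and equal SDs of 6.0 at both visits (assumed), expected change alters by 0.30 to 0.35 points per baseline point. Missing women one SD (6 points) away from the others at baseline would then differ by 1.8 to 2.1 points in change, in either direction.

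**Type I error.** At 2%/8% and g = 4, bias is 0.24 and SE about 0.41. With no true effect the two-sided rejection rate is about 9% (0.093 in 10,000 simulated trials). At 5%/15% and g = 4 it is about 16%, but overall loss is then 10%, above the plan's ceiling.

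**Could it overturn 2.8?** At 5% missing per arm, significance is lost only if bias reaches 2.8 − 1.96 × 0.41 = 2.0. If carried by the missing short-course women alone, they would have to be 2.0/0.05 = 40 points worse than assumed, ten times the SD of change.

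**LOCF.** The schedule reads "QoL will be assessed at baseline, 6 months, 12" and then 18 months, so the only score before month 6 is baseline. LOCF therefore sets the change to exactly zero. With 5% missing in both arms, 2.8 becomes 2.8 × 0.95 = 2.66. With no true effect, a 2%/8% split and the 3.1-point decline cited in Section 10b for another cancer, it creates a difference of (0.98 − 0.92) × (−3.1) = −0.19 even when dropout is completely random.

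**Mean imputation.** Filling in the arm mean returns the complete-case estimate and adds patients without adding variance. The SE is multiplied by about 1 − 0.05 = 0.95. The nominal 5% test becomes 2 × [1 − Φ(1.96 × 0.95)] = 0.063.

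**The case against.** The plan is more careful than the exclusion rule alone suggests. It admits that random missingness cannot be verified, and four of its six checks escape the criticism above: worst-case, best-case, multiple imputation, and a joint model meant for informative dropout. Retention is actively managed. There is a gift card for each questionnaire, up to five central and three site contact attempts (Section 8.1), and questionnaires continue after clinician withdrawal or an arm switch (Section 8). No 6-month distant-recurrence rate is given, so the size of that route is unknown. All of this stands, and it keeps the point modest.

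A reader might infer three stronger things that the documents do not support:

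- That the primary result is valid only if data are missing completely at random within age group. The model also contains arm, and bias is zero whenever fraction × gap is the same in both arms, even if dropout depends on health.
- That the weak checks expose the primary contrast. Sensitivity analyses cannot bias a primary estimate; the exposure comes from the complete-case rule.
- That informative dropout is not addressed. It is, though only as sensitivity work, with no imputation variables named, no definition of worst and best case by arm, and no rule for disagreeing results.

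**Conclusion.** The point holds in a limited form. The stated population and the exclusion rule conflict and must be reconciled, and the complete-case model does not handle missingness related to baseline PWB or health. Within the plan's 5% ceiling the bias ranges from zero (equal, similar dropout) to roughly 0.1 to 0.5 points (2%/8% split, gaps of 2 to 8 points), reaching 0.8 in the most extreme split tried. The comparison is with a planned 2.8 and a cited meaningful change of 2.

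This can distort the estimate, or produce a false positive when the true effect is small. It is unlikely to overturn a true 2.8-point effect, so it would be wrong to infer that the trial's main conclusion is in doubt on this ground. It matters more if dropout exceeds 5%. The sizes rest on assumed splits and gaps and on the plan's SD of 4.0.

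**What to change.** - Reconcile the population statement with the missing-data rule in Section 10b.
- Name in advance one primary estimator, either the planned multiple imputation or the planned random-effects model, and report its 6-month contrast. Include all randomised women, arm, age group, baseline PWB and the 12- and 18-month scores. State how PWB after death is treated.
- Keep the complete-case ANCOVA as a sensitivity analysis.
- Replace LOCF and mean imputation with delta-adjusted multiple imputation that worsens imputed short-course values stepwise until the conclusion changes.
- Keep the joint model and the worst- and best-case analyses. Define the latter by arm, and say how disagreement between analyses will be interpreted.

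The cost is SAP wording and modest programming, with no new data. The primary estimate would then rest on a missing-at-random assumption. It would also do little for women withdrawn before 6 months for distant recurrence, who contribute only baseline data. For them, the delta-adjusted and joint-model analyses must carry the assessment of informative dropout.

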5.3 Stratification Factors and Treatment Assignment

400 patients will be randomized 1:1 into either Arm 1 (short-course PMRT) or Arm 2 (long-course PMRT).

Randomization will be stratified by treatment center and age of the patient (<45 vs. ≥45).

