We hypothesize that patients randomized to short-course radiation will have increased satisfaction with their reconstruction as measured by the BREAST-Q reconstruction survey. We

will use a two-sample t-test for the BREAST-Q satisfaction score, and a chi-square test for 2x2 tables for post-decision regret. We consider a difference of 10 points in the BREAST-Q satisfaction score to be clinically meaningful. With the given total sample size of 400 (200 per arm), we will be able to detect this difference with 80% or higher power at a two-sided 0.05 significance level, if the standard deviation of the score is equal to or smaller than 35.6.

Strategy for handling missing data in other QoL analysis: To assess the robustness of our results, we will perform several sensitivity analyses as well as complete case analysis. For example, we will perform worst-case or best-case imputation or generalized linear modeling in combination with multiple imputation⁵¹ methodology.

Patient-centered outcomes analysis: Furthermore, we will also consider a new outcome that integrates tailored patient-prioritized quality of life measurement. As seen in our patient survey, the relative importance of QoL domains vary from patient to patient. At the baseline visit, we will ask each patient to give a weight to each FACT-B subscale based on its importance for her. We will then calculate a “weighted” total score of FACT-B (37 items) for each individual, using these weights. The weights will be standardized for each patient, so that the range of the weighted score can match with that of the FACT-B total score. We will perform the same analyses described above to assess the impact of the intervention on this exploratory new outcome that may enhance the measurement of patient-centered outcomes.

10c. Statistical analysis plan for clinical and oncologic outcomes and power consideration

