The primary analysis and power: We hypothesize that hypofractionated (short-course) radiation therapy has a higher reconstruction success rate, compared to the conventional fractionation (long-course) radiation at 18-months. We will use Chi-square test for 2x2 table to test this superiority hypothesis. We will also construct a two-sided 95% confidence interval for the difference in the composite outcome of reconstruction success likelihood (defined as no major complications, presence of reconstruction, and good or excellent cosmetic outcome). Recent estimates of reconstruction success after implant reconstruction and conventional radiation reveal a 71% likelihood at the 2-year time period.⁴⁶ “**Table: Effect size and power for superiority tests**” shows the available power with various reconstruction success probabilities for hypofractionation (short-course treatment), given the sample size of 400 patients. Variables that may affect outcomes such as chemotherapy regimen, endocrine therapy and patient age will be assessed for impact to ensure balance between both treatment arms.

Table: Effect size and power for superiority tests		
Reconstruction Success Likelihood (%)		Power (%)
Long-course radiation	Short-course radiation	
71.0	82.8	80
71.0	84.4	90

N=400 randomized patients and α (two-sided)=0.05

[figure not shown]
Data monitoring of local/regional recurrence event:

We will also follow oncologic outcomes to exclude any unexpected increase in the risk of recurrence with hypofractionation (short-course) radiation therapy, although a detectable increase in recurrence rates is unlikely given data from prior experiences of hypofractionation. The cumulative incidence of local or regional recurrence in a recent series of post-mastectomy

radiation therapy is about 2% at 18 months.³ Therefore, in the case where the recurrence rate is suggested to be statistically significantly greater than 2%, the study will be suspended to allow for investigation.

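### BREAST-Q is compared without its scheduled baseline score and reconstruction success without the randomization strata: both tests are valid, but they give up precision that costs nothing to keep

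*Combined protocol and SAP*

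**What the plan says.** **Randomization.** Section 5.3: "Randomization will be stratified by treatment center and age of the patient", split at 45 years, with 400 patients allocated 1:1. Section 10a expects 40% of patients in the younger group.

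**Reconstruction success (Section 10c, at 18 months).** "We will use Chi-square test for 2x2 table to test this superiority hypothesis". A two-sided 95% interval for the difference is added, with no strata named. Age, chemotherapy and endocrine therapy are mentioned only as variables to be looked at for balance. Recent estimates for conventional treatment "reveal a 71% likelihood at the 2-year time period". The power table gives 80% for 71.0% versus 82.8% and 90% for 71.0% versus 84.4%, under "N=400 randomized patients and α (two-sided)=0.05".

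**BREAST-Q (Section 10b, Other QoL analysis).** The study team "will use a two-sample t-test for the BREAST-Q satisfaction score". No baseline term, stratification factor or timepoint is named. "We consider a difference of 10 points in the BREAST-Q satisfaction score to be clinically meaningful"; at least 80% power is claimed for that difference if the SD does not exceed 35.6.

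**Collection of BREAST-Q.** The Section 8 schedule places participant questionnaires at baseline and at 6, 12 and 18 months, and BREAST-Q is among their instruments. Only the treatment-burden items are limited to a single timepoint.

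**Contrast with the primary endpoint.** For the FACT-B Physical Well-Being (PWB) score, Section 10b analyzes change from baseline and puts age group in an ANCOVA. The longitudinal models in the same section are named for FACT-B only.

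**The concern.** A baseline score that predicts the follow-up score removes part of the between-patient variation, so leaving it out of a randomized comparison widens the interval. Randomizing within strata balances the arms on those factors. A test that then ignores them computes its standard error as if that balance had not been arranged, so it is somewhat conservative when the factors are prognostic.

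The plan itself gives reasons to expect such effects. It expects long-course PWB scores of 19.0 and 24.0 in the two age groups, lists age in Section 10e among attributes that may relate to outcome, and leaves bolus, target delineation and most coverage decisions to physicians or institutions. It adjusts PWB for baseline and age but does neither for BREAST-Q, which is on the same visit schedule. What is at stake is efficiency on two non-primary endpoints, and a covariate choice that would otherwise have to be made after the data are seen.

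**Working it through.** **Inputs from the documents.** 200 per arm; two-sided alpha 0.05; 71.0% versus 82.8% or 84.4% (Section 10c); BREAST-Q difference 10 and limiting SD 35.6 (Section 10b); 40% under 45 (Section 10a).

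**Assumed, because the documents do not give them.** Baseline-to-follow-up correlation ρ for BREAST-Q, 0.2 to 0.7 (the 0.65 to 0.7 in Section 10b is for PWB); BREAST-Q SDs below 35.6; number of centers, 8 to 25; permuted blocks of 4; age odds ratio 1 to about 4.5; between-center SD on the logit scale, 0 to 0.8.

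**1. Reproduce the plan's figures.**

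Reconstruction success: power = Φ{[d − 1.96·√(2p̄(1−p̄)/n)] / √(p₁(1−p₁)/n + p₂(1−p₂)/n)}.
- 82.8%: d = 0.118, p̄ = 0.769; (0.118 − 1.96 × 0.04215)/0.04173 = 0.848; power 80.2%.
- 84.4%: d = 0.134, p̄ = 0.777; (0.134 − 1.96 × 0.04163)/0.04108 = 1.276; power 89.9%.

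BREAST-Q: power = Φ{Δ/(SD·√(2/n)) − 1.96} = Φ(10/3.56 − 1.96) = Φ(0.849) = 80.2% (80.0% by noncentral t).

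All three stated powers are right for the tests as planned.

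**2. BREAST-Q with baseline in the model.** The residual SD is SD·√(1−ρ²). At SD 35.6:

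| ρ | residual SD | power | 95% CI half-width |
|---|---|---|---|
| 0 (t-test) | 35.60 | 80.2% | 6.98 |
| 0.2 | 34.88 | 81.8% | 6.84 |
| 0.3 | 33.96 | 83.8% | 6.66 |
| 0.5 | 30.83 | 90.0% | 6.04 |
| 0.7 | 25.42 | 97.6% | 4.98 |

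Half-width = 1.96 × residual SD × √(2/200). At ρ = 0.5 the interval is 13% narrower (√0.75 = 0.866).

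At an assumed SD of 30, 25 or 20 the plain t-test already has 91.5%, 97.9% or 99.9% power. The power gain shrinks accordingly, but the proportional narrowing of the interval is unchanged.

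An unadjusted change score is not an equivalent fix. Its SD is 35.6·√(2(1−ρ)), which at ρ = 0.3 is 42.1 and gives 66% power, below the plain t-test. It breaks even only at ρ = 0.5.

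**3. Reconstruction success, stratified against unstratified.** Simulation with blocks of 4 within center × age and marginal rates held at 71% and 82.8% (6,000 trials per row, except 4,000 in the 12-center rows; Monte Carlo standard error about 0.5 to 0.6 points):

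| centers | age odds ratio | center SD | chi-square | CMH |
|---|---|---|---|---|
| 16 | 1 | 0 | 80.4% | 80.1% |
| 16 | 1.5 | 0 | 80.3% | 80.0% |
| 16 | 2 | 0 | 80.7% | 81.0% |
| 16 | 3 | 0 | 80.9% | 82.1% |
| 16 | 2 | 0.5 | 81.0% | 82.0% |
| 8 | 2 | 0.5 | 80.0% | 81.7% |
| 25 | 2 | 0.5 | 80.8% | 81.9% |
| 16 | 3 | 0.8 | 82.4% | 85.6% |
| 12 | about 2.7 (log 1.0) | 0.5 | 81.8% | 83.6% |
| 12 | about 4.5 (log 1.5) | 0.8 | 82.2% | 85.7% |

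The gain runs from about zero to about 4 points, and is 1 to 2 points or less unless centers differ strongly.

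**4. Type I error.** Under the null with age odds ratio 2 and center SD 0.5 (16 centers), the chi-square rejected 4.5% and CMH 5.4%. With log odds ratio 1.0 and center SD 0.5 (12 centers), the chi-square rejected 4.7%. Only at the strongest combination (odds ratio about 4.5, center SD 0.8) did its size fall to about 3.3%.

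**The case against.** The strongest reply is that nothing here is invalid. Both tests control type I error, their powers are stated correctly, and PWB is the primary endpoint of the trial. All of that stands.

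The BREAST-Q gain is also quoted at the worst SD the plan tolerates, with correlations the documents never supply. That stands too, and is why the gain is shown as a range and the smaller-SD results are given beside it.

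The baseline covariate is less certain than the schedule suggests. Section 8 describes a post-operative module that includes items on changes after radiation, and the baseline questionnaire is not enclosed (Appendix D). The schedule does imply that BREAST-Q is given before radiation, but the team should confirm that the satisfaction scale is on that form.

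Age is not wholly ignored: Section 10c looks at its balance and Section 10e describes treatment differences by age group. Neither enters the test or its interval.

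A reader might infer that ignoring the strata pulls the reconstruction test well below its stated 80%. A simulation can appear to show this if the odds ratio implied by 71% and 82.8% is fixed within strata and stratum effects are then added. Doing so lowers the marginal short-course rate to 82.1% under the moderate 12-center effects above, or 81.3% under the strong ones. By the formula in step 1, an unstratified test at those rates has only 74.7% or 67.7% power, so the fall comes from a smaller treatment difference than Section 10c states. At the plan's own rates the chi-square keeps its 80%.

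**Conclusion.** The point holds as one of efficiency, not validity. For BREAST-Q the gain can be material: about 2 to 17 points of power at SD 35.6 for ρ from 0.2 to 0.7, and 10 points at ρ = 0.5. It is small in power terms if the SD is 25 or less, where the interval still narrows. For reconstruction success the gain is about 0 to 4 points, and the planned chi-square is mildly conservative under moderate stratum effects.

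The documents do not support reading either test as invalid, either stated power as wrong, or BREAST-Q as underpowered: 35.6 is a ceiling SD, not an expected one. The sizes rest on an assumed BREAST-Q correlation and SD, and on assumed center numbers, block size and age and center effects.

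**What to change.** - **BREAST-Q satisfaction:** make the main analysis an ANCOVA of the follow-up score at one named timepoint on arm, baseline score, age group and center. Do not substitute an unadjusted change score.
- **Reconstruction success:** test with Cochran-Mantel-Haenszel by age group and center, and report a stratified risk difference with its 95% interval. Set the rule for pooling small centers before the data are seen.
- **Supportive analyses:** keep the two-sample t-test and the 2x2 chi-square.
- **Check:** confirm that the baseline questionnaire carries the BREAST-Q satisfaction scale.

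The cost is SAP wording, a pooling rule and slightly more analysis work. No new data and no change in sample size are needed. If the strata turn out not to be prognostic, stratifying costs almost nothing (80.4% versus 80.1% in the simulation).
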